7. ASSESSMENTS

Every effort should be made to ensure that protocol-required tests and procedures are completed as described. However, it is anticipated that from time to time there may be circumstances, outside the control of the investigator that may make it unfeasible to perform the test. In these cases, the investigator must take all steps necessary to ensure the safety and well-being of the subject. When a protocol-required test cannot be performed, the investigator will document the reason for the missed test and any corrective and preventative actions that he or she has taken to ensure that required processes are adhered to as soon as possible. The study team must be informed of these incidents in a timely manner.

7.1. Part 1 and 2

7.1.1. Safety

7.1.1.1. Laboratory Tests

The following safety laboratory tests will be performed at times defined in the STUDY PROCEDURES section of this protocol. Additional laboratory results may be reported on these samples as a result of the method of analysis or the type of analyzer used by the clinical laboratory; or as derived from calculated values. These additional tests would not require additional collection of blood. Unscheduled clinical labs may be obtained at any time during the study to assess any perceived safety concerns.

Table 4. Laboratory Tests

PF-06817024

Hematology	Chemistry	Urinalysis	Other
Hemoglobin	BUN/urea and Creatinine	рН	FSH ^b
Hematocrit	Glucose (fasting)	Glucose (qual)	HCG ^c
RBC count	Calcium	Protein (qual)	Urine drug screening ^d
MCV	Sodium	Blood (qual)	HIV, HBsAg, HBcAb,
MCH	Potassium	Ketones	and HCVAb ^e
MCHC	Chloride	Nitrites	HBsAb ^f
Platelet count	Total CO ₂ (Bicarbonate)	Leukocyte esterase	Phadiatop ^e
WBC count	AST, ALT	Urobilinogen	QuantiFERON-TB Gold
Total neutrophils	Total Bilirubin	Urine bilirubin	Test ^e
(Abs)	Alkaline phosphatase	Microscopy ^a	
Eosinophils (Abs)	Uric acid		
Monocytes (Abs)	Albumin		
Basophils (Abs)	Total protein		
Lymphocytes (Abs)			
	Additional Tests (Needed		
	for Hy's law)		
	AST, ALT (repeat)		
	Total bilirubin (repeat)		
	Albumin (repeat)		
	Alkaline phosphatase		
	(repeat)		
	Direct bilirubin		
	Indirect bilirubin		
	Creatine kinase		
	GGT		
	PT/INR		

- a. Only if urine dipstick is positive for blood, protein, nitrites or leukocyte esterase.
- b. At Screening only, in females who are amenorrheic for at least 12 consecutive months.
- c. HCG (human chorionic gonadotropin) for female subjects of childbearing potential who have a documented bilateral tubal ligation or bilateral salpingectomy (Part 2 only)
- d. At Screening, Day 0, and Day 31 (screening and Day 0 only for SAD cohorts).
- e. At screening only. Phadiatop collection for Part 1 only; starting with Cohort 5 and later, Phadiatop is to be collected prior to dosing.
- f. HBsAb test if screening results for HBsAg are negative and HBcAb are positive (for Part 1 (Cohort 5 and later) and Part 2.
 - *Part 1*: Minimum requirement for drug screening includes: cocaine, tetrahydrocannabinol (THC), opiates/opioids, benzodiazepines and amphetamines.
 - *Part 2*: Minimum requirement for drug screening includes: cocaine, opiates/opioids, benzodiazepines and amphetamines.
 - Subjects may undergo random urine drug screening at the discretion of the investigator. Drug screening conducted prior to dosing must be negative for subjects to receive study medication.

7.1.1.2. Pregnancy Testing (Part 2)

For female subjects of childbearing potential, a serum or urine pregnancy test, with sensitivity of at least 25 mIU/mL, will be performed at Screening, admission or Day 1 of all study periods, and follow-up visits. Results will be obtained prior to dosing during each period.

A negative pregnancy result is required before the subject may receive the investigational product. Pregnancy tests will also be done whenever one menstrual cycle is missed during the active treatment period (or when potential pregnancy is otherwise suspected), Pregnancy tests may also be repeated as per request of institutional review boards (IRBs)/ ethics committees (ECs) or if required by local regulations.

In the case of a positive confirmed pregnancy, the subject will be withdrawn from administration of investigational product but may remain in the study.

7.1.1.3. Physical Examinations

Physical examinations may be conducted by a physician, trained physician's assistant, or nurse practitioner as acceptable according to local regulation. A full physical examination will include head, ears, eyes, nose, mouth, skin, heart and lung examinations, lymph nodes, gastrointestinal, musculoskeletal, and neurological systems. The limited or abbreviated physical examination will be focused on general appearance including skin (specific attention to infusion and injection site reactions), the respiratory, gastrointestinal, and cardiovascular systems, as well as towards subject reported symptoms.

For measuring weight, a scale with appropriate range and resolution is used and must be placed on a stable, flat surface. Subjects must remove shoes, bulky layers of clothing, and jackets so that only light clothing remains. They must also remove the contents of their pockets and remain still during measurement of weight.

7.1.1.4. Blood Pressure and Pulse Rate

Blood pressure and pulse rate will be measured at times specified in STUDY PROCEDURES section of this protocol. Additional collection times, or changes to collection times of blood pressure and pulse rate will be permitted, as necessary, to ensure appropriate collection of safety data.

Supine blood pressure will be measured with the subject's arm supported at the level of the heart and recorded to the nearest mm Hg after approximately 5 minutes of rest. The same arm (preferably the dominant arm) will be used throughout the study. Blood pressure should not be taken from the arm with an intravenous infusion. Subjects should be instructed not to speak during measurements.

The same properly sized and calibrated blood pressure cuff will be used to measure blood pressure each time. The use of an automated device for measuring BP and pulse rate is acceptable, although, when done manually, pulse rate will be measured in the brachial/radial artery for at least 30 seconds. When the timing of these measurements coincides with a blood collection, blood pressure and pulse rate should be obtained prior to the nominal time of the blood collection.

7.1.1.5. Respiratory Rate

Respiratory rate will be measured after approximately 5 minutes rest in supine position by observing and counting the respirations of the subject for 30 seconds and multiplied by 2. When blood pressure is to be taken at the same time, respiration measurement will be done during the 5 minutes of rest and before blood pressure measurement.

7.1.1.6. Temperature

Temperature will be measured orally. No eating, drinking or smoking is allowed for 15 minutes prior to the measurement.

7.1.1.7. Electrocardiogram

Electrocardiograms (ECGs) should be collected at times specified in the STUDY PROCEDURES section of this protocol.

All scheduled ECGs should be performed after the subject has rested quietly for at least 10 minutes in a supine position.

Triplicate 12-lead ECGs will be obtained approximately 2-4 minutes apart during clinical confinement at times specified in the SoA. Single ECGs will be collected at all other designated visits per SoA. The average of the triplicate ECG measurements collected pre-dose on Day 1 will serve as each subject's baseline QTc value. When the timing of these measurements coincides with a blood collection, the ECG should be obtained prior to the nominal time of the blood collection, blood pressure and pulse rate.

To ensure safety of the subjects, a qualified individual at the investigator site will make comparisons to baseline measurements. If the QTc interval for single ECG collections is increased by \geq 45 msec from the baseline, or an absolute QTc value is \geq 500 msec for any scheduled ECG, then 2 additional ECGs will be collected, approximately 2-4 minutes apart, to confirm the original measurement. If either of the QTc values from these repeated ECGs remains above the threshold value (\geq 45 msec from the baseline; or is \geq 500 msec), then a single ECG must be repeated at least hourly until QTc values from 2 successive ECGs fall below the threshold value that triggered the repeat measurement.

For triplicate ECGs, if the average of QTc values from the triplicate measurements remains above the threshold value (≥45 msec from the baseline; or is ≥500 msec), then a single ECG must be repeated at least hourly until QTc values from 2 successive ECGs fall below the threshold value that triggered the repeat measurement.

If QTc values remain \geq 500 msec (or \geq 45 msec from the baseline) for greater than 4 hours (or sooner at the discretion of the investigator); or QTc intervals get progressively longer, the subject should undergo continuous ECG monitoring. A cardiologist should be consulted if QTc intervals do not return to less than 500 msec (or to \leq 45 msec above the baseline) after 8 hours of monitoring (or sooner at the discretion of the investigator).

In some cases, it may be appropriate to repeat abnormal ECGs to rule out improper lead placement as contributing to the ECG abnormality. It is important that leads are placed in the same positions each time in order to achieve precise ECG recordings. If a machine-read QTc value is prolonged, as defined above, repeat measurements may not be necessary if a qualified physician's interpretation determines that the QTc values are in the acceptable range.

7.1.1.8. Continuous Cardiac Monitoring by Telemetry

All abnormal rhythms will be recorded and reviewed by the study physician for the presence of rhythms of potential clinical concern. The time, duration, and description of the clinically significant event will be recorded in the CRF/DCT. In addition, a printed record of the tracing(s) of the clinically significant rhythm(s) will be made and retained with other source documents.

Telemetry should be collected using a centralized system that also allows for the storage and advanced analysis of all recorded data in order to preserve important events for future evaluations. Holter monitoring should not be used in parallel with continuous telemetry, unless it is the only means of data storage available at the study site, or verifiable arrhythmia quantification is required. To establish a baseline, telemetry should be recorded for at least 2 hours before dosing. This may be done immediately prior to dosing or at some 2-hour continuous interval in the 24 hours prior to dosing, as long as the recording is performed when the subject is awake. Telemetry may be stopped within a reasonably short period of time prior to dosing, in order to avoid interference with study operations conducted immediately before dosing. However, it is expected that the telemetry leads will be in place and the system connected prior to dosing.

7.1.1.9. Infusion and Injection Site Reaction Assessment

Subjects will be monitored for signs of any infusion site reactions including but not limited to erythema, swelling, bruising, pain or pruritus as times specified in the SoA.

Subject enrolled in to the SC single dose cohort will be monitored for signs of injection site reactions included but not limited to erythema, swelling, skin ulceration, pain or pruritus.

Any signs or symptoms related to either an infusion or injection site reaction should be treated according to the Investigator's standard of care and reported as adverse events.

7.1.2. Pharmacokinetic, Immunogenicity, CCI Samples

All samples will be collected according to the times outlined in the SoA. Details regarding the collection, processing, storage and shipping of the blood samples will be provided to the investigator site prior to initiation of the study. Samples will be analyzed using a validated analytical method in compliance with Pfizer standard operating procedures for PK, Anti-PF-06817024 ADA and NAb analysis;

The samples must be processed and shipped as indicated to maintain sample integrity. Any deviations from the processing steps (eg, sample collection and processing steps, interim storage or shipping conditions), including any actions taken, must be documented and reported to the sponsor. On a case-by-case basis, the sponsor may make a determination as to whether sample integrity has been compromised. Any deviation from the specified sample handling procedure resulted in compromised sample integrity, will be considered a protocol deviation

As part of understanding the pharmacokinetics, and immunogenicity of the study drug, samples may be used for further characterization and/or evaluation of the bioanalytical method.

PK and immunogenicity samples from subjects receiving placebo will not be routinely analyzed.

7.1.3. Pharmacokinetics (PK) for PF-06817024

Blood samples (4 mL) to provide a minimum of 1.5 mL serum for pharmacokinetic analysis will be collected into appropriately labeled tubes containing no anticoagulant or gel serum separator at times specified in the SoA section of the protocol.

The actual times for sample collection may change but the number of samples will remain the same. All efforts will be made to obtain the pharmacokinetic samples at the exact nominal time relative to dosing. However, samples obtained within 10% of the nominal time (eg, within 6 minutes of a 60 minute sample) from dosing will not be captured as a protocol deviation, as long as the exact time of the sample collection is noted on the source document and data collection tool (eg, CRF/DCT).

7.1.4. Immunogenicity

Blood samples (4 mL) to provide a minimum of 1.5 mL serum for ADA and NAb analysis will be collected into appropriately labeled tubes containing no anticoagulant or gel serum separator.

Samples will be analyzed using a validated analytical method in compliance with Pfizer/vendor standard operating procedures (SOPs). Samples determined to be positive for ADA may be further characterized for NAb.

7.1.9. Blood Volume

The total blood sampling volume for individual subjects in Part 1 of this study is approximately 690.5 mL for those in the SAD portion (from Screening through Day 211) and approximately 835 mL for those in the multiple dose component (from Screening through Day 241). The total blood sampling volume for individual subjects in Part 2 of this study (from Screening through Day 211) is approximately 624 mL. Table 5 and Table 6 reflect approximate sample volumes needed for each measured endpoint. The actual collection times of blood sampling may change, but the total blood volume collected will not increase. Additional blood samples may be taken for safety assessments at times specified by Pfizer, provided the total volume taken during the study does not exceed 550 mL during any period of 30 consecutive days.

Table 5. Blood Volume for Part 1

Sample Type	Sample	Number of Sampling Times			Total Volume
	Volume	Screening	Study Period	Follow-Up Visits	(mL)
	(mL)		(SAD/multiple	(SAD/multiple	(SAD/multiple
			dose)	dose)	dose)
Safety Labs	7	1	5/10	10/8	112/133
(including					
hematology,					
serology, chemistry					
and FSH)					
QuantiFERON TB	3	1	0	0	3
Gold Test					
Phadiatop	4	1	0	0	4
PK	4	0	10/20	10/8	80/112
CCI					
	_	_	_	_	_
		_			
			1/6	0.40	10/11
Immunogenicity	4	0	1/3	9/8	40/44
(ADA, NAb)					
CCI					
TOTAL					690.5/835

SAD = Single ascending dose; TB = Tuberculosis.

This total volume does not include discarded blood from pre-draws used to remove fluid from flushed catheters or extended follow-up visits, if applicable. Each extended follow-up visit will increase the Total Blood Volume by 11 mL per visit.

Number of Sampling Times Total Volume Sample Type Sample Volume (mL) Screening Study Period Follow-Up (mL) Visits 7 2 84 Safety Labs (including 1 hematology, serology, chemistry, HCG and FSH) QuantiFERON TB Gold Test 3 0 0 3 PK 0 64 Immunogenicity (ADA, 0 32 NAb) TOTAL

Table 6. Blood Volume for Part 2

TB = Tuberculosis.

This total volume does not include discarded blood from pre-draws used to remove fluid from flushed catheters or extended follow-up visits, if applicable. Each extended follow-up visit will increase the Total Blood Volume by 13 mL per visit.

7.1.9.1. Potential Cases of Acute Kidney Injury

Abnormal values in serum creatinine (SCr) concurrent with absence of increase in blood urea nitrogen (BUN) that meet the criteria below, in the absence of other causes of kidney injury, are considered potential cases of acute kidney injury and should be considered important medical events.

An increase of ≥ 0.3 mg/dL (or ≥ 26.5 µmol/L) in serum creatinine relative to subjects' own baseline measurement should trigger another assessment of SCr as soon as practically feasible, preferably within 48-hours from awareness

If the second assessment (after the 1st observations of \geq 0.3 mg/dL (or \geq 26.5 μ mol/L) in serum creatinine relative to subjects' own baseline measurement) is \geq 0.4 mg/dL (or \geq 35.4 μ mol/L), the subject should be discontinued from the study and adequate, immediate, supportive measures taken to correct apparent acute kidney injury

Subjects should return to the investigational site and be evaluated as soon as possible, preferably within 48-hours from awareness of the second assessment confirming abnormal SCr result. This evaluation should include laboratory tests, detailed history, and physical assessment. In addition to repeating SCr, laboratory tests should include: serum

blood-urea-nitrogen, serum creatine kinase, serum electrolytes (including at a minimum potassium, sodium, phosphate/phosphorus, calcium), in addition to urinary dipstick, urine microscopic examination, and urinary indices. All cases confirmed on repeat testing as meeting the laboratory criteria for acute-kidney-injury, with no other cause(s) of laboratory abnormalities identified should be considered as potential cases of drug-induced kidney injury irrespective of availability of all the results of the investigations performed to determine etiology of the abnormal SCr. If ≥ 2 subjects in the same cohort are noted to have $2 \ \underline{consecutive}$ SCr results of $\geq 0.3 \ mg/dL$ (or $\geq 26.5 \ \mu mol/L$), an assessment of whether the finding may be considered adverse drug reaction should be undertaken.

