Part 3 is a placebo-controlled, double blind, pharmacist and sponsor open, cohort to evaluate safety, tolerability, PK, immunogenicity, of repeat doses of PF-06817024 administered to subjects with moderate to severe AD. Approximately 20 subjects are planned to be enrolled in this cohort. Subjects will be randomized to receive PF-06817024 or placebo in a 3: 1 ratio (PF-06817024: placebo). Additional subjects up to a total of approximately 32 may be enrolled in a 3: 1 ratio (PF-06817024: placebo).

Subjects randomized to PF-06817024 will receive a loading dose of 600 mg IV on Day 1, followed by 3 doses of 300 mg IV every 4 weeks (last dose being on Week 12). Placebo subjects will receive 4 IV doses of matching placebo every 4 weeks. This dosing regimen is expected to decrease the time to steady state

exposure and provide nearly complete target coverage based on currently available in vitro and clinical data.

1.3.1.3. Parts 1, 2, and 3

The duration of the follow-up is selected to be at least 1 year after the last dose of study drug (at Week 12 for Part 3), which is ≥ 3 times the preliminary estimated half-life of approximately 90 days and > 80% exposure (AUC) based on emerging data for the earlier cohorts of healthy subjects, which is adequate to estimate the elimination half-life. If the emerging data project that pharmacologically relevant exposure will extend significantly longer than 1 year, the subjects will be asked to return for extended follow-up visit(s) at up to 3 month intervals beyond the last planned regular visit until one of the following criteria has been met:

• The follow up period from the last dose of study drug is approximately ≥5 times the observed half-life; OR

• The period since the last dose of study drug is of sufficient duration to have projected exposures decrease below ADA drug tolerance levels; OR

The Sponsor will inform the sites when subjects may be discharged from the study based on review of emerging data indicating that one or more of the above criteria are met. Current guidance is that subjects will be in the study for 5 half-lives ie, about 450 days from the last dose.

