7.2.1.2. Pregnancy Testing

For female subjects of childbearing potential, a serum or urine pregnancy test with sensitivity of at least 25 mIU/mL, will be performed at Screening, all study periods (Week 0, Week 1, Week 4, Week 8, Week 12, Week 16), follow-up (Week 20, Week 24, Week 36, Week 48) and extended follow-up visits. Results will be obtained prior to dosing during each period. A negative pregnancy result is required before the subject may receive the investigational product. In addition, urine pregnancy tests must be done at home by female subjects of childbearing potential at the nominal visits corresponding to Week 28, Week 32, Week 40 and Week 44 and every month between the scheduled extended visit follow-up visits. PI must be informed immediately if pregnancy test is positive and must see the PI for retesting. Pregnancy tests will also be done whenever one menstrual cycle is missed during the active treatment period (or when potential pregnancy is otherwise suspected). Pregnancy tests may also be repeated as per request of institutional review boards (IRBs)/ ethics committees (ECs) or if required by local regulations.

Pregnancy testing MUST have been performed within the permitted window and the result MUST be negative for female subjects of childbearing potential prior to dosing. Pregnancy test results will be documented in the CRF.

In the case of a positive confirmed pregnancy, the subject will be withdrawn from administration of investigational product but may remain in the study.

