8.2. Reporting Period

For SAEs, the active reporting period to Pfizer or its designated representative begins from the time that the subject provides informed consent, which is obtained prior to the subject's participation in the study, ie, prior to undergoing any study-related procedure and/or receiving investigational product, through the end of the study. SAEs occurring to a subject after the active reporting period has ended should be reported to the sponsor if the investigator becomes aware of them; at a minimum, all SAEs that the investigator believes have at least a reasonable possibility of being related to investigational product are to be reported to the Sponsor.

AEs (serious and nonserious) should be recorded on the CRF/DCT from the time the subject has taken at least 1 dose of investigational product through the subject's last visit.

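### The acute-kidney-injury rule uses a BUN condition in its definition but creatinine alone in its steps, and it ends study participation where the plan calls for about 450 days of follow-up

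*Protocol*

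**What the plan says.** Protocol Section 7.1.9.1 opens with a definition. "Abnormal values in serum creatinine (SCr) concurrent with absence of increase in blood urea nitrogen (BUN) that meet the criteria below", where no other cause of kidney injury is present, "are considered potential cases of acute kidney injury and should be considered important medical events".

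The operational steps follow:

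- A rise of ≥0.3 mg/dL (≥26.5 µmol/L) "in serum creatinine relative to subjects' own baseline measurement should trigger another assessment of SCr as soon as practically feasible".
- If the second value is ≥0.4 mg/dL (≥35.4 µmol/L), "the subject should be discontinued from the study and adequate, immediate, supportive measures taken to correct apparent acute kidney injury".
- A site evaluation follows, "preferably within 48-hours from awareness of the second assessment confirming abnormal SCr result". BUN is one of the tests listed for it.
- Cases confirmed against the laboratory criteria, with no other cause found, count as potential drug-induced kidney injury.
- Two or more subjects in a cohort with two consecutive results of ≥0.3 mg/dL prompt a review of whether the finding is an adverse drug reaction.

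Section 7.2.5.1 applies all of this to Part 3 by cross-reference.

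On follow-up, Section 1.3.1.3 states: "Current guidance is that subjects will be in the study for 5 half-lives ie, about 450 days from the last dose". Section 8.2 has AEs recorded from "at least 1 dose of investigational product through the subject's last visit". Section 2.2.1 sets the primary endpoints (TEAEs, SAEs, laboratory, vital-sign and ECG abnormalities) up to study end. Sections 6.1.2.12 and 6.2.6 keep subjects who ask to stop treatment in follow-up. For a confirmed pregnancy, Section 7.2.1.2 (and likewise 7.1.1.2 for Part 2) says "the subject will be withdrawn from administration of investigational product but may remain in the study".

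**The concern.** Two parts of the rule do not fit together or with the rest of the protocol.

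First, the definition depends on BUN not rising, and the steps do not look at BUN. Classification has consequences. An event judged an important medical event under Section 8.6 is reported as serious. Section 8.14.1 then sets a 24-hour notice, and in Part 1 a treatment-emergent SAE on active drug pauses dosing (Section 3.2). SAE incidence and causality are primary endpoints. If two sites read the definition differently, the same laboratory picture can be counted differently.

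Second, the action at ≥0.4 mg/dL refers to the study and not to dosing. Taken literally, scheduled laboratory, PK, immunogenicity and AE visits stop because of a safety outcome, while a long-lived antibody is still present. The missing data would then depend on the quantity that the study sets out to measure.

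**Working it through.** **1. Which steps use BUN.**

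| Element of Section 7.1.9.1 | Creatinine | BUN condition |
|---|---|---|
| Definition, important-medical-event status | yes | yes: no increase |
| Repeat test | rise ≥0.3 mg/dL | none |
| Discontinuation | second value ≥0.4 mg/dL | none |
| Site work-up | confirmed abnormal value | measured, not a condition |
| Drug-induced label | refers back to the laboratory criteria | unclear |
| Two-subject review | two values ≥0.3 mg/dL | none |

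Take a subject with creatinine up 0.5 mg/dL on both tests and BUN also up. The subject is retested, passes the 0.4 step, is discontinued and is worked up, yet fails the opening definition. The same creatinine with unchanged BUN meets it, if no other cause is present. The section gives no size or reference value for a BUN increase, so how much of a rise excludes a case is also open. SAP Section 6.2.2 has no renal rule; it refers laboratory review to sponsor standards.

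**2. Rise or absolute value.** The first trigger is explicitly a rise from the subject's own baseline. At the ≥0.4 step, baseline is mentioned only in the bracket describing the first observation. The two-subject rule omits it. The paired units agree (assumed factor 88.4: 0.3 × 88.4 = 26.5; 0.4 × 88.4 = 35.4) but do not settle the question.

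**3. The plan's own follow-up figure.** 5 half-lives × 90 days = 450 days, as stated. Mean single-dose half-lives in healthy subjects are about 79–94 days, and 108 days after a second 100 mg dose in four subjects (Section 1.2.5.2). Five half-lives at 79, 94 and 108 days are 395, 470 and 540 days.

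**4. Drug remaining and follow-up forgone in Part 3.** Doses fall on Days 1, 29, 57 and 85. The share of the last dose remaining is 2^(−t/half-life), a single-exponential approximation. Days forgone = 450 − t.

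| Discontinued at | Days since last dose (t) | Remaining, half-life 90 days (79 to 108) | Days forgone |
|---|---|---|---|
| Day 29, 57 or 85 (before that day's dose), or Day 113 | 28 | 80.6% (78.2–83.6%) | 422 |
| Day 253 | 168 | 27.4% (22.9–34.0%) | 282 |
| Day 337 | 252 | 14.4% (11.0–19.8%) | 198 |

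**5. What still applies after discontinuation.** The 48-hour evaluation stands. Sections 6.1.2.12 and 6.2.6 list an early-withdrawal visit with safety laboratory tests and PK (and, in Part 3, immunogenicity and AE questioning), but both say that leaving those procedures undone is not a deviation provided safety was preserved. Section 8.1 says only that AE follow-up to resolution may be needed.

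**The case against.** The strongest reply is that nothing is overlooked. A reader might infer from the definition that cases with raised BUN are missed. The documents do not support that. Both analytes are in the routine panel (Tables 4 and 7), every operational step runs on creatinine, and abnormal chemistry is itself a primary endpoint. Section 8.5 makes a result reportable as an AE if it calls for further diagnostic testing or leads to discontinuation. Section 8.6 also lets an event be judged medically important on its merits. This stands: what is uncertain is the label, not detection. Nor do the documents rank renal cases by BUN, so they give no ground for saying that the excluded cases are the gravest.

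A reader might also infer that all confirmed cases leave and that nothing more is collected. Neither is right. A repeat rise of 0.3 to below 0.4 mg/dL triggers no discontinuation, and the safeguards in step 5 remain. Section 8.2 also asks for later SAEs to be reported if the investigator learns of them. Those safeguards are only partly binding.

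A third tempting argument is scale. At the February 2018 cut-off, 49 + 20 = 69 of 71 dosed subjects were in Parts 1 and 2, mostly single-dose, so discontinuation could seldom avert exposure. But those parts had already been followed for up to about 1–2 years. Their scheduled safety laboratory tests end at Day 211 or 241 and are discretionary afterwards. A single-dose case at Day 32 would lose 211 − 32 = 179 days of scheduled laboratory tests, not the whole 450-day period. Part 3 is the relevant setting, and there doses do remain to be stopped during treatment.

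Finally, the protocol allows withdrawal from the study for safety, and pregnancy is a different event, so different handling may be deliberate. That is fair, but a discretionary power does not say what this fixed instruction means or what follow-up continues.

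Reading the two-subject rule as an absolute value is strained, since the section twice ties ≥0.3 mg/dL to baseline. The omission looks editorial. The documents give no figure for how many subjects would meet an absolute reading.

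**Conclusion.** The point holds as an inconsistency to be reconciled. Section 7.1.9.1 can discontinue a subject for apparent kidney injury who does not meet its own definition of a potential case, which leaves the important-medical-event and drug-induced labels unclear. Its removal of subjects from the study does not fit Section 1.3.1.3, the primary endpoints up to study end, or the sections that separate stopping drug from leaving.

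On the protocol's own half-life, a Part 3 subject discontinued 28 days after a dose has about 81% of that dose remaining (78–84%) and forgoes about 422 of 450 days. These figures assume single-exponential decline, half-lives in atopic dermatitis like those in healthy subjects (as Section 1.3.2.3 also assumes), and a literal reading of discontinuation. The safety summary shown in Section 1.2.5.1 names no renal case, so the loss is a risk built into the wording and not an observed one. The study tests no hypotheses, so no power or error rate is affected.

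**What to change.** At the next amendment, the sponsor should:

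1. Reconcile the BUN clause with the creatinine-only steps, so that definition, triggers and classification in Section 7.1.9.1 rest on one stated criterion. If BUN stays in it, say what counts as an increase.
2. Reconcile the discontinuation wording with Sections 1.3.1.3, 6.1.2.12, 6.2.6, 7.1.1.2, 7.2.1.2 and 8.2. State whether it means dosing or study participation, and which safety follow-up continues.
3. State whether the ≥0.4 mg/dL step and the two-subject ≥0.3 mg/dL rule are rises from the subject's own baseline, as the first trigger is.

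The choice of renal criterion and of stopping rule is the sponsor's. The cost is a wording change centred on one section and, depending on the choice made, some added attendance at visits already scheduled.
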